5.4.2 Primary endpoint

The study is powered as a non-inferiority analysis of distress associated with streamlined genetic education and testing versus traditional pre-test genetic counseling and testing.

A two sample one-sided t-test is used to check the non-inferiority for the experimental treatment in terms of the MICRA (Multidimensional Cancer Risk Assessment questionnaire). We assumed the mean MICRA scores for both experimental arm and control arm will be the same and equal to 13.5, with a common standard deviation of 8.4. These values were obtained from a study that assessed the MICRA in a similar patient population [25]. Using these estimates, a total sample size of 102 (51 patients each arm) will provide 80% power to detect the non-inferiority for the experimental treatment with a significance level of 0.05 and a non-inferiority margin of 4.2 (50% standard deviation). This margin was chosen as a high general MICRA score has previously been considered to be one standard of deviation above the mean; thus, we are taking a more conservative approach by using a non-inferiority margin of 0.5 the expected standard deviation observed in Cella et al [28]. When incorporating a potential 10% attrition rate, the total sample size will be 112.

5.4.3 Secondary endpoints

Resource utilization

Mean resource utilization will also be compared between the two models using summary statistics.

Genetic testing uptake

Genetic testing uptake between the two groups will be compared using logistic regression.

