As evidenced by this discussion, a model that achieves the goal of increasing uptake and decreasing resource utilization while not significantly increasing patient distress has yet to be established. We hypothesize that a streamlined model of service delivery will not have a detrimental effect on patient distress with the counseling and testing process. We also hypothesize that this model will adhere to near-universal testing uptake without increasing cost burden on the healthcare system. This would be the first randomized trial to investigate the safety and non-inferiority of this promising new genetic service delivery model, providing an alternate, resource-effective method of pre-test education that could improve genetic testing uptake without increasing adverse psychological effects.

2. Study Objectives

Primary Objective

a. To determine if implementation of a streamlined model of genetic service delivery increases patient distress as measured by the Multidimensional Impact of Cancer Risk Assessment Scale when compared to the traditional model of counseling [25].

Hypothesis: An expedited education and testing model in this patient population will not decrease patient satisfaction with genetic counseling or increase patient anxiety.

Secondary Objectives

a. To compare cost between the traditional genetic counseling model and the streamlined model.

Hypothesis: An expedited education and testing model in this patient population will be less expensive compared to the traditional model.

b. To compare genetic testing uptake between the streamlined and traditional models.

Hypothesis: In this study setting, both groups will have close to universal testing uptake.

c. To observe differences in distress throughout the genetic education and testing process, including pre-education, post-education, and post-results disclosure.

Hypothesis: The process of genetic education, testing and results review causes minimal distress in patients.

3. Study Design

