3.4 Study population

The study will recruit from the gynecologic oncology clinic at Duke Cancer Institute and **collaborating institutions**. A maximum of 112 patients will be consented.

4. Study Procedure

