4.3 Risk and Benefit Assessment

4.3.1 *Risk*

- The first risk associated with this proposed study includes the use of secure medical records. To ensure that patient confidentiality is maintained, all data retrieval will be performed by the principal investigator or assigned researchers using password-secured computers. Each subject will be assigned a subject ID code that will be linked to the medical record number. This will be generated using REDCap database and will be stored on a standalone database server hosted by Duke Health Technology Services (DHTS) and will only be accessible to the key personnel of this study. Collaborating sites will share the same Duke REDCap.
- Risks of genetic testing will also be associated with the study, as a majority of patients in both arms will likely undergo testing. However, this is a risk associated with a separate, well-established standard of care in this population rather than with the study intervention. Thus, while it will be addressed with the patient when they complete their separate, standard consent for genetic testing, it is not considered to be an incremental risk of this study.
- The study also incurs a potential incremental risk of adverse psychological reactions to streamlined genetic counseling and testing. Our hypothesis is that the streamlined model will not significantly increase patient distress with the genetic counseling and testing process.

4.3.2 *Benefit*

- Patients will receive genetic risk assessment, which is currently recommended for everyone in this patient population. There is no other direct benefit provided to

subjects included in this study. However, we hope that the findings of this study will lead to increase analysis and uptake of expedited models of genetic education and testing, thus potentially benefiting this patient population and their family members.

4.3.3 *Cost*

Charge of testing and face-to-face post-test counseling will be billed as per usual. The only incremental cost incurred by the participant will be the time spent participating in trial activities. Traditional pre-test counseling is not currently billed at Duke Cancer Institute, nor would the streamline education process be.

4.3.4 *Compensation*

- No compensation will be provided for participation in this trial.

5. Study Design

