5.3 Outcome Variables

5.3.1 Demographic information

Measurement time: Baseline

Description: Demographic information, including cancer history, age, race, marital status, and income will be collected from each participant upon enrollment.

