5.4 Statistical Methods

5.4.1 Demographic and Baseline Survey Information

The SG and TG will be compared at baseline regarding demographic information, medical and family history and baseline distress as measured by the Impact of Events Scale. Categorical variables will be tested using the Chi-Square test. Continuous variables will be assessed using the Student T test or the Mann-Whitney U test for non-normal data. Equality of variance across these variables will be assessed. Any variables with a significant difference greater than $p=0.1$ will be controlled for in future analyses.

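### Uptake is predicted to be near-universal in both arms, where the odds ratio from the planned logistic regression may not be finite, and section 5.4.3 names no other estimate

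*Combined protocol and SAP*

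**What the plan says.** Section 2, Secondary Objective b, is to compare testing uptake between the two models. Its hypothesis is "In this study setting, both groups will have close to universal testing uptake". The Purpose of study paragraph in section 1 says the same of the streamlined model: "We also hypothesize that this model will adhere to near-universal testing uptake". No percentage is given anywhere; section 4.3.1 says only that "a majority of patients in both arms will likely undergo testing".

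The method is one sentence in section 5.4.3: "Genetic testing uptake between the two groups will be compared using logistic regression". It names no effect measure, test statistic or interval, and no rule for an arm in which everyone is tested. The chi-square test in section 5.4.1 is for baseline comparisons. That section also says that imbalanced baseline variables "will be controlled for in future analyses", which could bring covariates into the uptake model.

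On size, section 3.4 says "A maximum of 112 patients will be consented", and section 5.4.2 plans 51 evaluable patients per arm.

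**The concern.** Logistic regression estimates a log odds ratio, which needs at least one tested and one untested patient in each arm. The nearer uptake comes to the predicted level, the more likely it is that an arm has no untested patient. The trial's own hypothesis therefore describes the setting in which its only named method is weakest.

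Two things are at stake. The first is the estimate: the report could carry an odds ratio with no finite value or no upper limit, and say little about how far apart the arms might be. The second is the p-value: Wald, likelihood-ratio and score tests all belong to the same model and can disagree sharply on the same table. With none named, the choice could be made after the data are seen.

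**Working it through.** **Inputs.** Arm sizes: 56 (112 / 2, equal split assumed, section 3.4) and 51 (section 5.4.2). The plan's sample size reproduces for MICRA: with margin 4.2, SD 8.4 and one-sided 5%, the noncentral t gives power 0.806 at 51 per arm, and 102 × 1.1 = 112.2. The plan has no power or precision figure for uptake to reproduce. Uptake rates below are assumptions.

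**Chance of a non-finite odds ratio.** An arm of n patients with true uptake p is full with probability p^n. With equal uptake, at least one arm is full with probability 1 − (1 − p^n)², and both are full with probability p^(2n). For example, 0.95^56 = 0.0566, and 1 − (1 − 0.0566)² = 0.110.

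| True uptake, both arms | At least one arm full (n = 56 / 51) | Both arms full (n = 56 / 51) |
|---|---|---|
| 90% | 0.5% / 0.9% | <0.1% / <0.1% |
| 95% | 11% / 14% | 0.3% / 0.5% |
| 97% | 33% / 38% | 3.3% / 4.5% |
| 98% | 54% / 59% | 10% / 13% |

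A non-finite odds ratio becomes the more likely result when p^n exceeds 1 − √0.5, that is, above 97.8% (n = 56) or 97.6% (n = 51). With unequal uptake of 98% and 90%, the chance is 32% / 36%.

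**Disagreement between tests.** Both binomials were enumerated exactly at a two-sided 5% level. Non-finite tables count as no Wald rejection, and two full arms as no rejection by any test.

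| Scenario | Wald | Likelihood ratio | Score (Pearson) |
|---|---|---|---|
| Type I error, 95% in both | 0.3% / 0.2% | 8.4% / 8.7% | 4.5% / 4.4% |
| Type I error, 97% in both | <0.1% / <0.1% | 9.0% / 8.6% | 3.3% / 2.9% |
| Power, 98% vs 90% | 9.4% / 6.3% | 53% / 50% | 43% / 39% |
| Power, 98% vs 95% | 0.3% / 0.2% | 20% / 19% | 11% / 9.6% |

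The likelihood-ratio power is not directly comparable, because that test exceeds its nominal level in this region.

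**Two illustrative tables.**

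- 56/56 vs 50/56: the fitted log odds ratio is 22.4 with SE about 17,500, so Wald p is about 0.999. The likelihood-ratio p is 0.003, the profile lower limit for the odds ratio is 2.9, and the score p is 0.012. The difference is 6/56 = 10.7 points (Miettinen-Nurminen 3.9 to 21.5).
- 55/56 vs 54/56: the odds ratio is (55 × 2)/(54 × 1) = 2.04 (0.18 to 23.1). It is finite but says little. The difference is 1/56 = 1.8 points (−6.3 to 10.6), and the Wilson intervals are 90.6-99.7% and 87.9-99.0%.

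**How the proposed estimate behaves.** Miettinen-Nurminen coverage was 93.5-99.8% over equal uptake of 95, 97, 98 and 99% and over 98 vs 90, 99 vs 90 and 98 vs 95. The interval agreed with the score test in every table. If both arms are full, the difference is 0 with a Newcombe interval of ±6.4 points (56) or ±7.0 points (51).

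**The case against.** The strongest reply is that section 5.4.3 names neither the odds ratio nor a Wald interval or test. The worst figures above therefore belong to one choice within the named method. This stands: they describe usual logistic output, not a commitment in the plan. What remains is that the plan does not say which output it will use.

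A reader might infer that the planned analysis yields nothing once an arm is full. That goes too far. With one full arm the model still gives a profile-likelihood bound on one side and a likelihood-ratio p-value, as the first table shows. Both share the inflation seen at 95-97% uptake, but they are not nothing. Only two full arms leave the odds ratio undefined.

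A reader might also infer that failure is likely. The documents do not support that, because they give no rate. Traditional-arm patients are tested at a visit about 2-4 weeks later (section 5.2.2), so losses before it would lower uptake among all randomised patients, although a streamlined arm near 100% would still carry the risk.

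Nor should the covariate rule in section 5.4.1 be counted as a further cause. In simulation with covariates unrelated to arm and outcome, adjustment made some coefficient infinite more often but did not change how often the arm odds ratio was finite.

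Finally, the plan never says that a non-significant odds ratio would prove near-universal uptake, and it sets no numerical threshold. Requiring one would add a decision rule that the protocol does not contain.

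**Conclusion.** The point holds as a mismatch between a predicted ceiling and an analysis with no stated effect measure, test or interval. Its size depends on an assumed uptake rate and on equal arms of 56 or 51: negligible at 90%, about one trial in eight at 95%, and more likely than not from about 98%. In the same region the unstated choice of test changes both the error rate and the conclusion. With both arms near the ceiling (98% vs 95%), score-test power is only 10-11%, so an interval tells the reader more than any test. The primary MICRA analysis and the sample size are unaffected. Priority is low; the case for acting is that the change is cheap.

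**What to change.** In section 5.4.3:

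- Make the main uptake analysis the difference in proportions, streamlined minus traditional, among all randomised patients, with a Miettinen-Nurminen 95% confidence interval. Newcombe is an acceptable, somewhat more conservative alternative.
- Report each arm's proportion with a Wilson 95% interval, which speaks directly to Secondary Objective b. No numerical threshold is needed.
- If a p-value is wanted, name the score (Pearson) test.
- If an odds ratio or covariate adjustment is kept, use Firth-penalised logistic regression as a supportive analysis.

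The cost is three or four sentences, with no new data or patients. The one downside is that the main uptake estimate is unadjusted. Section 5.4.3 should state that this is an exception to the adjustment rule in section 5.4.1.

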5.4.4 Exploratory endpoints

Impact of Events Scale

Mean changes in the Impact of Events Scale scores between each administration point will be compared between the two arms using the Wilcoxon rank sums test.

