5.2 Study Procedures (See Figure One)

5.2.1 *Baseline Questionnaires (Both Groups)*

- After randomization, each subject will complete a series of baseline questionnaires on a tablet in the gynecologic oncology clinic, entering their results directly into the secure REDCap database. These baseline questionnaires include a basic numeracy test, the baseline anxiety and distress survey (IES) and the demographic information questionnaire, which will include questions concerning age, race, marital status, home address, and income [26,27].

5.2.2 *Tradition Counseling Group (TG)*

a. Formal Consultation Scheduling

- After completion of baseline surveys, the TG subjects will be referred to a formal pre-test consultation with a genetic counselor that will be scheduled for a date approximately 2-4 weeks after their primary appointment (for patients in whom results will determine treatment, appointments will likely be expedited). They will be made aware of the date and time of this appointment prior to leaving their initial visit.

b. Electronic Family History Questionnaire

- TG subjects will complete an electronic family history questionnaire (FHQ) within one week of the primary visit. This is a system already employed by the Duke Clinical Genetics Department. An email is sent to the subject's primary email account with a link to a secure, HIPAA compliant portal, in which the subject can then enter her family cancer history.
- A member of the genetics team will curate the results by contacting the subject to review common errors and clarify any ambiguities in the pedigree.

c. Formal Consultation and Post-Counseling Distress Survey

- The TG subjects will then meet with the genetic counselor at the previously scheduled appointment time. During this visit, they will receive approximately thirty to sixty minutes of counseling regarding genetic testing and potential results. The discussion is based on the ASCO and NCCN guidelines of informed consent for genetic testing.
- After counseling, participants will be given the option to undergo a multi-gene panel genetic test either via saliva or blood sample. Those who agree to testing will also complete the standard genetic testing consent form. As per standard practice of the clinical genetic service at DCI, patients will also be asked to provide consent for somatic tumor testing of surgical specimen (non-cytologic).

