5.2.3 Streamlined Group (SG)

a. Video-Assisted Genetic Education

- After completion of the baseline surveys, the SG subjects will watch an approximately eight minute long genetics education video. This video will be made with the assistance of Duke University genetic counselors and gynecologic oncology providers. It will consist of a discussion of genes and mutations, the recommendation of universal testing for high grade epithelial ovarian cancer, a review of genes associated with ovarian cancer predisposition, the possibility of uncertain results including variants of undetermined significance, the potential for undetected mutations in known or unknown cancer susceptibility genes, the potential impact on personal treatment and on family members, the possibility of genetic discrimination and the legal protection of genetic information.
- After watching the video, the primary oncologic provider will then offer multi-gene panel testing.
- All subjects will then have the option to "opt out" and receive formal genetic counseling prior to making a decision about testing.
- If the subject elects to undergo genetic testing, she will fill out the standard genetic testing consent form. As per standard practice of the clinical genetic service at DCI, patients will also be asked to provide consent for somatic tumor testing of surgical specimen (non-cytologic).

b. Electronic Family History Questionnaire

- SG subjects will complete an electronic family history questionnaire (FHQ) within one week of the primary visit. This is a system already employed by the Duke Clinical Genetics Department. An email is sent to the subject's primary email account with a link to a secure, HIPAA compliant portal, in which the subject can then enter her family cancer history.
- A member of the genetics team will curate the results by contacting the subject to review common errors and clarify any ambiguities in the pedigree.

c. Post-education distress measurement

- Subjects will complete a post-education distress and anxiety survey (IES) via an email link to a confidential REDCap survey link within one week of formal consultation.

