5.3.4 Anxiety and depression

Measurement time: Baseline, post-education and post-results disclosure

Description: The Impact of Events Scale (IES) has been used widely as a means of measuring patient distress (particularly intrusive thoughts or avoidance) over a defined incident [27]. This evaluation will be used to identify trends in anxiety or depression in both arms throughout the education and testing process. In this trial, the "incident" will be described as "the risk of my cancer being hereditary."

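### The exploratory IES comparison uses unadjusted change scores, with baseline IES not a prespecified covariate and one contrast starting from a score the assigned arm can already have affected

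*Combined protocol and SAP*

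**What the plan says.** Section 5.3.4 sets three IES administrations: "Baseline, post-education and post-results disclosure". The first is completed in clinic, after randomisation and before any education (section 5.2.1: "After randomization, each subject will complete a series of baseline questionnaires on a tablet"). The second follows the randomised education in both arms; for the streamlined group (SG) the text is "Subjects will complete a post-education distress and anxiety survey (IES) via an email link", and the traditional group (TG) has a matching step after its consultation.

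Section 5.4.4 gives the whole analysis, a Wilcoxon rank-sum test, in one sentence: "Mean changes in the Impact of Events Scale scores between each administration point will be compared between the two arms". It names no covariate, effect estimate, confidence interval or significance level. It does not say whether the change from baseline to post-results is tested as well as the two consecutive steps.

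Two other places bear on this. Section 5.4.1 compares the arms at baseline, including "baseline distress as measured by the Impact of Events Scale", and says that variables flagged at a p = 0.1 threshold will be adjusted for later. Section 2 lists the matching aim as secondary objective c: "To observe differences in distress throughout the genetic education and testing process, including pre-education, post-education, and post-results disclosure". Section 5.4.4 files the same comparison under exploratory endpoints.

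**The concern.** There are three difficulties.

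- **Starting point of the last contrast.** The post-education score is taken after the randomised education, so the assigned arm can already have changed it. An arm left more distressed by its education has further to fall, and the fall counts in its favour.
- **Use of baseline.** Subtracting baseline fixes its coefficient at 1. Fitting it as a covariate estimates the coefficient and usually gives a more precise arm difference, at no cost in data.
- **Fit between sections.** Section 5.4.1 may call for baseline IES to be adjusted for, and a plain rank-sum test has no place for a covariate. Section 5.4.4 also speaks of mean changes, while a rank-sum test does not compare means and yields no mean difference.

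The MICRA is measured only after results. The IES is therefore the only planned between-arm evidence on distress before results, and section 4.3.1 names adverse psychological reaction to the streamlined process as a potential incremental risk of the study.

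**Working it through.** **Inputs from the documents.** There are three IES time points (5.3.4) and 51 patients per arm (5.4.2). No IES mean, SD, correlation, distribution or target difference is given.

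**The plan's own figure.** The only sample size is for the MICRA: margin 4.2, SD 8.4, true difference 0, one-sided 0.05, 80% power. The normal approximation gives 2 × (1.645 + 0.842)² × (8.4/4.2)² = 49.5, or 50 per arm. With the noncentral t, power is 79.9% at 50 and 80.6% at 51 per arm. The stated 51 reproduces, and nothing below alters it.

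**Starting point of the last contrast.** Suppose SG is 5 points worse than TG after education and the arms are equal at baseline and after results. The SG minus TG differences in change are:

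- baseline to post-education: 5 − 0 = +5 (SG worse);
- post-education to post-results: 0 − 5 = −5 (SG apparently better);
- baseline to post-results: 0 − 0 = 0.

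Now take 5 points as 0.5 SD, with normal scores, equal correlation r between all three scores, 51 per arm and two-sided 0.05. Simulation (3,000 trials per setting) gives:

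| r | Last step significant in favour of SG | First step significant against SG |
|---|---|---|
| 0.3 | 52.5% | 53.2% |
| 0.5 | 69.1% | 68.8% |
| 0.7 | 87.6% | 87.8% |

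If SG is still 0.2 SD worse after results, the last step nevertheless favours SG significantly in 22%, 31% and 46% of trials.

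**Change score against covariate adjustment.** With equal SD s at both times, the per-patient variance is 2(1 − r)s² for a raw change and (1 − r²)s² after baseline adjustment. The ratio of adjusted to raw is (1 + r)/2: 0.65, 0.75 and 0.85 at r = 0.3, 0.5 and 0.7.

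Power for an assumed 0.5 SD difference, normal scores, 51 per arm, two-sided 0.05 (ranges are across separate simulations):

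| r | Rank-sum on change | ANCOVA |
|---|---|---|
| 0.3 | 53–55% | 73–74% |
| 0.5 | 68–70% | 81–82% |
| 0.7 | 88–89% | 93–94% |
| 0.8 | 97.2% | 99.0% |

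Almost all the loss comes from the raw change. Under normality the rank test costs only 1 to 2 points against a t-test on the same change.

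**Skewed scores.** With strongly right-skewed (lognormal) scores and the same shift, the order reverses for untransformed ANCOVA. Rank-sum on change has 79.6%, 91.6% and 98.6% power, against 75.4%, 80.0% and 89.5%; here r = 0.3, 0.5 and 0.7 is the correlation before the lognormal transformation. Rank-based ANCOVA (ranks of follow-up on ranks of baseline) keeps the gain from adjustment: at r = 0.5 it has about 99% against 92% for rank-sum on change. It was ahead of rank-sum on change in every setting with a true difference that was simulated, both normal and skewed.

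**The case against.** The case for the plan has real force.

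- **Baseline is used.** A reader might infer that the plan ignores baseline IES. It does not: any change from baseline subtracts it, and section 5.4.1 has a conditional adjustment rule. What stands is narrower. Baseline IES is not a prespecified covariate, the rule depends on a baseline significance test, and the named test cannot apply it.
- **Power loss is not general.** A reader might infer that the rank-sum plan is underpowered as such. The documents give no IES figures to support that. The loss is small at r = 0.8, and under strong skew the planned test beats untransformed ANCOVA. What stands is the case for baseline adjustment on a suitable scale.
- **Early harm is not hidden.** The baseline to post-education contrast is reported too, and in the example it shows SG 5 points worse. Step-by-step changes also suit the stated aim of following trends (5.3.4). The risk lies in reading the last contrast alone, and the plan gives no rule for reading the contrasts together.
- **Harm concentrated in mutation carriers.** A reader might argue that rank-sum is weak because distress will rise sharply in the 23–28% with a mutation (18% plus 5–10%, Background). If 25% of SG rose by 2 SD, power at r = 0.5 would indeed be about 46% against 66% for ANCOVA. But no woman knows her result at the post-education survey, so this cannot support the argument about distress before results.
- **Missing scores.** A reader might infer that one missing IES removes a woman from two of three comparisons. The text does not settle whether there are two or three, and a missing baseline would also cost data in a baseline-adjusted model unless imputed.

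**Conclusion.** The concern holds in limited form. The IES analysis is an unadjusted comparison of raw changes in which baseline is not a prespecified covariate. The section 5.4.1 adjustment rule cannot be carried out with the test named in 5.4.4. The post-education to post-results contrast can credit an arm for recovering from distress that its own education caused; that follows by arithmetic and needs no distributional assumption.

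The efficiency loss is conditional. Under normal scores and a 0.5 SD difference it is roughly 20 power points at r = 0.3, 12 to 14 at r = 0.5, 5 at r = 0.7 and 2 at r = 0.8. The effect size, correlation and distribution are all assumptions. Under strong skew the benefit of adjustment depends on choosing a rank-based or transformed scale.

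Severity is minor. Section 5.4.4 labels the comparison exploratory and attaches no decision rule to it, and the primary MICRA test and sample size are untouched. Its status should still be reconciled with secondary objective c.

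**What to change.** In section 5.4.4:

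1. Analyse the post-education and post-results IES scores adjusted for baseline IES in all patients, whatever the baseline test shows. Use ANCOVA at each visit or one repeated-measures model with arm, visit, arm-by-visit and baseline IES.
2. Report the adjusted SG minus TG difference with a 95% CI at each visit.
3. Prespecify a rank-based ANCOVA or a transformation for skewed scores.
4. Label the post-education to post-results change descriptive.
5. State whether the comparison is secondary or exploratory, and make section 2 and section 5.4.4 agree.

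The cost is a few sentences, slightly more programming and a choice of scale to make in advance. No new data are needed.

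### The one planned analysis of change in the Impact of Events Scale compares arms only, so it cannot test the hypothesis that the process causes minimal distress

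*Combined protocol and SAP*

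**What the plan says.** Section 2 of the combined protocol and SAP lists as secondary objective c: "To observe differences in distress throughout the genetic education and testing process, including pre-education, post-education, and post-results disclosure". Its hypothesis reads: "The process of genetic education, testing and results review causes minimal distress in patients".

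Section 5.3.4 schedules the IES at baseline, post-education and post-results disclosure. It says the scale will be "used to identify trends in anxiety or depression in both arms throughout the education and testing process", and names no method for doing so.

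Section 5.4.4, headed as exploratory, gives the only analysis of IES change: mean changes between administrations "will be compared between the two arms using the Wilcoxon rank sums test". Section 5.4.1 also uses the IES, but only to compare the arms at baseline.

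**The concern.** The objective, its hypothesis and the purpose stated in Section 5.3.4 all concern what happens to patients over time. The stated test concerns whether one arm changes more than the other. These are different questions, and a trial can answer the second while saying nothing about the first.

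The IES is the only distress measure with a baseline. MICRA is collected once, after results (Section 5.3.5), so it cannot show change. Section 4.3.1 names adverse psychological reactions to the streamlined process as a potential incremental risk. If the test is non-significant and no interval or threshold is given, the plan offers no formal basis for saying that distress stayed low, and none for saying that it did not.

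**Working it through.** **Inputs.** Three IES administrations (Section 5.3.4); 51 evaluable patients per arm, 102 in total (Section 5.4.2); rank-sum test on changes (Section 5.4.4). The documents give no IES standard deviation, so everything below is in units of the SD of the change score. The rises are assumptions, shown as a range, and all 102 women are assumed to have complete IES pairs.

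**The plan's own figure.** The only sample size given is for MICRA. With margin 4.2, SD 8.4 and 51 per arm, the noncentrality is 4.2 / (8.4 × √(2/51)) = 2.52 on 100 degrees of freedom. A one-sided 0.05 t-test then has 80.6% power, which agrees with the stated 80%. No figure is stated for the IES.

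**What the test can see.** Let D be each woman's change over an interval. The rank-sum statistic depends only on the ranks of D in the combined sample. Replacing every D by D + c leaves all ranks, and so the p-value, as they were. As a check, adding 0, 5 or 20 to every value in two simulated samples of 51 gave p = 0.973 each time.

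**Illustration.** 10,000 simulated trials with normal changes, 51 per arm, the same rise in both arms, two-sided 0.05:

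| Common rise (SD of change) | Rank-sum rejects | Paired t, one arm (n = 51) | Paired t, pooled (n = 102) |
|---|---|---|---|
| 0 | 5.1% | 5.1% | 4.8% |
| 0.25 | 4.7% | 42% | 71% |
| 0.5 | 5.3% | 94% | >99% |
| 1 | 5.4% | 100% | 100% |
| 2 | 5.0% | 100% | 100% |

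The rank-sum column is the type I error rate throughout. It restates the algebra and does not measure an effect. The other columns show what the same data could detect.

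**Precision available.** The 95% CI half-width for a mean change is t(0.975, n − 1) / √n:
- per arm: 2.009 / √51 = 0.28 SD
- pooled: 1.984 / √102 = 0.20 SD

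For the between-arm difference in mean change it is 1.984 × √(2/51) = 0.39 SD.

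**Does another section fill the gap?** Section 5.4.1 is a single-time comparison at baseline, Section 5.4.2 is MICRA after results, and Section 5.4.3 covers resource use and testing uptake. None specifies a within-arm change, an interval for it, a model over time or a criterion for minimal.

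**The case against.** The best defence is that objective c and Section 5.3.4 are descriptive: one sets out to observe, the other to identify trends. Section 5.4.4 names mean changes between administrations, which have to be calculated by arm and would probably be reported. In a two-arm trial, a between-arm difference in change is also a fair reading of differences in distress, and the rank-sum test addresses it validly. The analysis is labelled exploratory.

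Much of this stands, and it rules out some stronger readings that a reader might infer:

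- *That the IES is analysed nowhere else, or that objective c is not addressed at all.* Section 5.4.1 compares baseline IES, and the planned test covers the between-arm part of the objective.
- *That a trial with a sharp rise in both arms would look the same as one with none.* Only the p-value would be the same; the mean changes, if shown, would differ visibly.
- *That the sponsor intends to read non-significance as minimal distress.* The documents do not say so.
- *That the hypothesis about patient anxiety is also left untested by this analysis.* That wording sits under the primary objective, which compares the two models, so a between-arm analysis suits it.

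The defence does not supply a method for the hypothesis under c. Mean changes without intervals or a threshold cannot support or contradict a claim that distress is minimal, and a rank test yields no interval for a mean difference. The exploratory label does not settle the matter either, because Section 2 lists the objective as secondary.

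**Conclusion.** The point holds in this form: the only stated analysis of IES change cannot test the hypothesis under secondary objective c, and cannot formally show the trends in both arms that Section 5.3.4 promises. The insensitivity to a common rise is exact and needs no assumption about IES scores.

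The precision figures (half-width about 0.28 SD per arm, 0.20 SD pooled) assume complete IES pairs in 102 women, a number that comes from the MICRA calculation. They cannot be turned into IES points without an SD. The powers in the table rest on assumed rises.

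A within-arm analysis has its own limit. There is no control group that goes without testing, and women join soon after diagnosis or as late as the start of a fourth chemotherapy cycle (Section 4.1.2). Change in the IES would show what happened during the process, not what the process caused.

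The primary MICRA analysis and the sample size are untouched. This is a gap in a secondary objective that is worth closing before the data are analysed.

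**What to change.** Amend Section 5.4.4 as follows.

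1. For each interval (baseline to post-education, post-education to post-results, baseline to post-results), report mean IES change with a 95% CI within each arm.
2. Alongside the rank-sum test, report the between-arm difference in mean change with a 95% CI.
3. If a repeated-measures model is used, enter baseline IES either as a covariate or as a response time point, not both.
4. State in advance what size of change counts as minimal, and judge it against the within-arm intervals. If the true change is zero, the upper limit centres on about 0.28 SD, so a threshold below that would be met less than half the time.
5. Word the conclusion as change during the process, and say that a non-significant between-arm test is not evidence of minimal distress.
6. Treat any pooled estimate as secondary. Traditional counselling comes about 2–4 weeks after the first visit (Section 5.2.2), whereas the video follows the baseline surveys (Section 5.2.3, Streamlined Group), so the intervals differ by arm.
7. Reconcile the secondary status of objective c in Section 2 with the exploratory heading of Section 5.4.4.

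The cost is some SAP wording and a little extra analysis of IES data that are already planned. No further patients, visits or questionnaires are needed.
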